Social support messages are an important part of close relationships (Cutrona & Suhr, 1992); however, recipients perceive some supportive messages to be unhelpful or unwanted (Floyd & Ray, 2017). In general, emotional support messages are viewed as a particularly useful form of support in the months following a cancer diagnosis (Arora et al., 2007). There are instances, though, of cancer patients viewing some emotional support messages negatively (Ray & Veluscek, 2017, 2018). Much of the prior research looking at peoples' reactions to emotional support messages have done so by looking for differences between high, moderate, and low-quality messages (High & Dillard, 2012), and have not considered the possibility that some offers of emotional support may contain both positive statements of empathy and caring and also negative statements of criticism and blame. Therefore, the present study investigates how cancer patients rate emotional support messages that consist of different percentages of positive and negative statements. Additionally, prior research has shown that some messages may be retained in memory for years after they are communicated (Knapp, Stohl, & Reardon, 1981), and some of these memorable messages can be classified as supportive messages (Wang, 2012). However, minimal research has focused on what is specifically remembered from supportive messages, particularly if those messages are composed of both positive and negative statements. Research by Ray and Veluscek (2017) has shown, though, that cancer patients can readily recall both positive and negative support messages received in the year after initial diagnosis and that receiving negative messages sometimes led to re-evaluating whether future updates would be shared with the supporter. Furthermore, the well-supported propensity for humans to pay greater attention and give more processing to negative information than positive information (Baumeister, 2001), would suggest that negative portions of ambivalent support messages would have a stronger influence on the recipient, particularly in terms of what is recalled (Bless, Hamilton, & Mackie, 1992; Finkenauer & Rimé, 1998). The present study tests this negativity bias and the findings will illuminate how cancer patients process, perceive, and recall emotional support messages that have both positive and negative components. To test the possible effects of negative portions of messages, 18 message conditions have been developed (see list provided under Participation heading). This results in a nested factorial design in which you have 5

message conditions (0, 20, 40, 60, or 80 percent negativity), 2 conditions based on the placement of the negative portions (beginning or end), and 2 versions of each message condition to allow for the messages to be analyzed as random factors. A 5x2x2 design typically yields 20 cells; however, when there is 0% negative portions of a message, it is unnecessary to consider the placement of the negative portions that do not exist. This results in 18 conditions as opposed to 20 conditions.

Study Purpose/Objective

To understand how cancer patients react to and recall emotional support messages that contain different percentages of positive statements of empathy and caring and also negative statements of criticism and blame.

Study Aims

Aim #1: To determine how cancer patients rate emotional support messages that consist of differing percentages of negative statements (0, 20, 40, 60, or 80 percent) and messages in which those negative portions occur at either the beginning or end of the supportive message.

Aim #2: To determine what portions of emotional support messages that consist of differing percentages of negative and positive statements cancer patients recall in the minutes after reading a message, and whether the placement of the negative portions at either the beginning or end of the message also affects recall.

Hypotheses & Research Questions

Hypotheses 1-4 and Research Questions 1-4 address Study Aim #1.

H1: Cancer patients' ratings of message effectiveness differ based on the percentage of the support message that is negative.

RQ1: How, if at all, do cancer patients' ratings of message effectiveness differ depending on whether negative portions of messages occur at the beginning or end of the entire message?

H2: Cancer patients' ratings of supporter competence differ based on the percentage of the support message that is negative.

RQ2: How, if at all, do cancer patients' ratings of supporter competence differ depending on whether negative portions of messages occur at the beginning or end of the entire message?

H3: Cancer patients' likelihood of seeking support from a supporter in the future differs based on the percentage of the support message that is negative.

RQ3: How, if at all, do cancer patients' likelihood of seeking support from a supporter in the future differ depending on whether negative portions of messages occur at the beginning or end of the entire message?

H4: Cancer patients' self-reports of emotional improvement after receiving a support message differs based on the percentage of the support message that is negative.

RQ4: How, if at all, do cancer patients' self-reports of emotional improvement after receiving a support message differ depending on whether negative portions of messages occur at the beginning or end of the entire message?

Hypotheses 5-7 address Study Aim #2.

H5: Cancer patients recall negative portions of supportive messages more frequently than they recall positive portions of supportive messages.

H6: As the percentage of negative portions of a supportive message increases, cancer patients likelihood to recall negative portions of supportive messages also increases.

H7: The number of negative words recalled from the supportive messages by cancer patients differ depending on the percentage of the message that is negative.

Methods

This is a cross-sectional, observational survey study. Data will be collected through a mass email disseminated through the online survey platform Qualtrics.

Recruitment and Eligibility

800 participants will be recruited from Moffitt TCC-consented patients who have agreed to be contacted for future research.

Inclusion Criteria: Living patients, 18 years of age or older, diagnosis of breast, prostate, thoracic, or digestive cancer in the past 3 years, consent to the Moffitt TCC protocol and indication of their willingness to be contacted for future research by including an email contact, and ability to read and write fluently in English.

A random selection of at least 800 patients who fit inclusion criteria will be drawn by Moffitt Collaborative Data Services. An invitation to participate in the current study will be sent to participants via an email disseminated through the online survey host Qualtrics. The contact list of email recipients will be uploaded into the Qualtrics system and the email will be sent from [name] (study team member). If a potential participant were to choose to reply to this email with questions about the study or for any other reason, these replies would be sent to [name], who would be tasked with responding to the potential participant's message. The invitation will include a description of the study and a link to the study survey.

Consent Process

Because participation will occur solely online and consists only of an online questionnaire, the research team requests a waiver for written consent. Instead, we request that consent can be given by having participants read an informed consent statement on the opening page of the online questionnaire. Clicking to the next page and beginning survey would signify consenting to participate.

Participation

Participating in the study consists of taking an online questionnaire. The questionnaire begins with self-reported demographic questions (biological sex, age, ethnicity, time since initial cancer diagnosis, cancer site). Next, the participant is asked to think of someone they know well but who they did not directly disclose the news of their cancer diagnosis. Then, the participant is told to imagine receiving a written message of support from this person in the days after initially being diagnosed with cancer. The participant then reads one of 18 different emotional support messages randomly assigned through the Qualtrics survey system. These 18 messages are each 100 words long and systematically vary in how much of the message is composed of negative statements of criticism and positive statements of caring. The 18 message conditions are part of a 5x2x2 nested factorial design and are as follows:

- Two messages composed of only positive statements (0% negative).
- Two messages in which the last 20% of the message consists of negative statements of criticism.
- Two message in which the first 20% of the message consists of negative statements of criticism.
- Two messages in which the last 40% of the message consists of negative statements of criticism.
- Two message in which the first 40% of the message consists of negative statements of criticism.
- Two messages in which the last 60% of the message consists of negative statements of criticism.
- Two message in which the first 60% of the message consists of negative statements of criticism.
- Two messages in which the last 80% of the message consists of negative statements of criticism.
- Two message in which the first 80% of the message consists of negative statements of criticism.

The participants then answer a series of closed ended scales regarding quality of the support message, the supporter's competence, the amount of emotional improvement they experienced after reading the message, and the likelihood to seek support from the person they chose earlier

in the survey in the future. Participants also answer an open-ended question in which they are asked what specific phrases or sentences they recall from the support message they read.

During pilot tests of the questionnaire, the average time to complete was 7.5 minutes. Three weekly reminders will be sent by email to those who have not completed the survey to encourage participation. Those who opt out will not be contacted with follow-up emails. The recruitment emails will include a link that can be clicked to opt out of the recruitment process for the study.

See Appendix A for the questionnaire and Appendix B for the message conditions.

Planned Analyses

The number of participants was determined through power analyses performed by the statistical software program G*POWER. The suggested sample size provided by G*POWER was 479. Specifically, this was determined by conducting an *a priori* analysis with an effect size (f) of .25, alpha error probability of .05, power ($1 - \beta$ error probability) of .95, and 18 groups, which is the total number of message conditions listed above. Importantly, a power analysis using these same parameters but for an ANCOVA also yielded a suggested samples size of 479.

Statistical analyses will consist of 5x2x2 nested factorial ANOVA models. The first study aim will be tested through 4 ANOVA models that will test for differences between participants who received the different messages in terms of 1) perceived message effectiveness, 2) perceptions of supporter competence, 3) likelihood to seek support from the supporter in the future, and 4) self-reports of emotional improvement. Depending on the correlations among the dependent variables, a MANOVA may be used instead of an ANOVA to test the first aim of the study. Similarly, if significant covariates (such as age or times since diagnosis) are found, the ANOVA/MANOVA could become an ANCOVA or MANCOVA. To test the second aim of the study, a chi-square analysis will test to see if participants recall negative portions of messages more frequently than positive portions of messages depending on which message they received (i.e., dependent on the position and percentage of the negative message portions). The second aim will also be tested using ANOVA models to determine if significant differences occurred in the number of negative words that were recalled across the 18 messages received (i.e., dependent on the position and percentage of the negative message portions). The software program LIWC (Linguistic Inquiry and Word Count) will be used determine the number of negative words recalled by the participants in their open-ended responses.

Potential Benefits

There are no benefits for being in this study; however, by joining this research study, the participant is helping to provide information which may help science and society.

Potential Risks

Because of the personal nature of the questions to be asked, the participant might reflect on unpleasant memories while completing the questionnaire. Although not expected to occur, it is

possible that a breach of confidentiality could occur if the computer on which the data file is stored is compromised or otherwise hacked or illegally accessed.

Compensation, Benefits, and Risks

At the end of the questionnaire, participants will be given the option to click a link to a separate Qualtrics survey where they can provide an email address to enter a lottery for one of five \$50 Visa e-Gift Cards. By having participants provide their email in a separate Qualtrics survey, the personal identifiable email data will be kept separate from the study data. The data from the Qualtrics survey will be stored in a password protected encrypted folder behind a university firewall that only the study team can access. The data for the drawings will be destroyed after the drawings have been conducted. The drawings will be conducted immediately following the end of data collection, which is expected to conclude by the end of 2019. The drawing will be conducted by a member of the research team, [name] of the School of Communication at San Diego State University. A total of five \$50 Visa e-Gift Cards will be given away. No participant will be able to win more than one of the five gift cards. The chances of winning a prize is approximately 1 in 120. The winner will be notified immediately by email in a message that also includes the instructions for activating their Visa e-Gift card.

The researchers expect the study to indirectly benefit society by generating new knowledge about emotional support following a cancer diagnosis. Individual participants are not expected to benefit either directly or indirectly from participating.

Participants will experience minimal if any risk at all. Because of the personal nature of some questions to be asked, the participant may reflect on unpleasant memories while completing the questionnaire. To protect their data, participants will be encouraged to do the questionnaire from a trusted, personal computer. The only other foreseeable potential risk is loss of privacy/breach of confidentiality if the data were to be accessed illegally by someone other than the research team. The safeguards against this possibility are discussed below.

Data Storage

The data will not be made available to members outside of the research team and will never be presented or published in such a way to identify a single participant. The SPSS dataset generated by Qualtrics and used for the statistical analyses will be deidentified.

Data will be saved in a password protected encrypted folder behind a university firewall that only the study team can access. Any data transfer will be done using encrypted, secure channels.

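### Do 800 recruited, 479 from the power analysis and lottery odds of 1 in 120 contradict one another?

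*Combined protocol and SAP*

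**What the plan says.** Recruitment and Eligibility says that "800 participants will be recruited from Moffitt TCC-consented patients who have agreed to be contacted for future research". The same section then describes the draw: "A random selection of at least 800 patients who fit inclusion criteria will be drawn". It uses the word participants for those who are only being invited: "An invitation to participate in the current study will be sent to participants via an email disseminated through the online survey host Qualtrics".

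Planned Analyses says "The number of participants was determined through power analyses performed by the statistical software program G*POWER" and then "The suggested sample size provided by G*POWER was 479". The inputs given are f = .25, alpha .05, power .95 and 18 groups, and an ANCOVA version is reported to give the same number. The figure 800 does not appear there.

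Compensation, Benefits, and Risks offers five cards. It states that "No participant will be able to win more than one of the five gift cards" and that "The chances of winning a prize is approximately 1 in 120". Entry is voluntary: after the questionnaire "participants will be given the option to click a link to a separate Qualtrics survey".

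The text available gives no response, completion or lottery-entry rate.

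**The concern.** Taken one sentence at a time, the plan seems to give three sizes: 800, 479 and, by implication, 600. The word participants covers both people who have merely been emailed and people counted in the power analysis. Each way of fixing the final sample leaves something loose:

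- If 800 are contacted, recruited is an imprecise word.
- If 800 complete, the total is 800 / 479 = 1.67 times the calculated size with no reason given, and the draw would have to exceed 800 unless everyone responds.
- If exactly 479 complete, odds of 1 in 120 cannot arise, because 479 entrants give about 1 in 96 and fewer entrants give better odds.

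At stake is whether a later reader can tell what size was planned and whether it was reached. A true contradiction could also hide a power shortfall.

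**Working it through.** **1. Reproduce the plan's figure.** The inputs from Planned Analyses are f = .25, alpha .05, power .95 and 18 groups. For a one-way fixed-effects omnibus F test:

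- df1 = 18 − 1 = 17 and df2 = N − 18
- noncentrality λ = N × f² = N × 0.0625
- power = P(noncentral F exceeds the 5% critical value)

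At N = 478 power is 0.9496. At N = 479, λ = 29.94, df2 = 461 and power is 0.9502. The smallest N reaching .95 is therefore 479, as stated. With one covariate (df2 = N − 19) the answer is again 479, which matches the plan's ANCOVA remark.

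**2. Entrants implied by the lottery.** With five prizes and at most one per person, the chance of winning is 5 / entrants. Setting this to 1/120 gives 5 × 120 = 600 entrants. Because entry is optional, 600 entrants means at least 600 completers.

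**3. Put the three numbers on one path.** If exactly 800 patients are contacted:

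- 479 completers need 479 / 800 = 59.9% response.
- 600 completers need 600 / 800 = 75% response; the true figure is higher if some completers do not enter the lottery.

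So 800 contacted, at least 600 completing and 479 required are mutually consistent.

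**4. Power if each number is the completed total** (same test, messages treated as fixed):

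| Completed surveys | Readers per message | Power | Odds if all enter |
|---|---|---|---|
| 479 | 26.6 | 0.950 | 1 in 96 |
| 600 | 33.3 | 0.987 | 1 in 120 |
| 800 | 44.4 | 0.999 | 1 in 160 |

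**5. Where a shortfall would begin.** Power is below .95 whenever fewer than 479 complete, however many are invited; 450 completers give 0.933. At exactly 800 invited, and with assumed response rates, 50% (400 completers) gives 0.892 and 40% (320) gives 0.784.

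**6. Which reading the text supports.** The Participation section calls the invitations recruitment emails, lets people opt out of the recruitment process, and plans three weekly reminders to those who have not finished. Recruitment there means the contact stage, and non-response is expected. That fits 800 as the number contacted.

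**The case for a change.** The strongest case for a change is that nobody should have to work out the expected sample from prize odds. No reading leaves every sentence exactly as it stands. Allowing at least 800 to be drawn does not say how many completed surveys are expected. And if contact stops at 800, the stated power depends on a response of about 60% that is nowhere justified.

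Part of this stands. The response rate is unstated, recruited is loosely used, and participants carries two meanings. A response below 60% of exactly 800 would leave the 18-group test short of its target, and a reader cannot judge from the text how likely that is.

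The rest does not carry. The benchmark is not lost: Planned Analyses states the power, effect size, alpha, group count and the 479 that results, so a reader can check whether at least 479 was reached. Only the intended margin above 479 is unclear. Low response is a risk in any email survey, and relabelling the numbers would not reduce it; the draw is already a minimum rather than a cap. The lottery figure is an approximate disclosure about prizes, not a sample-size statement.

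**Conclusion.** This is missing detail, not a contradiction, and no change follows. No stated calculation is wrong: 479 reproduces exactly, and the odds correspond to 600 entrants, which lies between the number required and the number contacted. Completed totals of 479, 600 and 800 all give at least 95% power on the plan's own test (0.950, 0.987 and 0.999). Writing down a response rate and replacing one word would leave the design, messages, analysis and data collection as they are. Analysts can sensibly take 479 as the minimum number of completed surveys and report the numbers contacted and completed.

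The conclusion rests on reading 800 as patients contacted, which the Participation section supports but does not state outright. The power figures assume f = .25 and fixed messages. The background section provides for analysing messages as random factors; power would then also depend on the number of messages, and these figures would not carry over. The consent pages and appendices were not available, so it cannot be checked whether they state an expected enrolment.

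### Does the plan need to name one placement test for RQ1-RQ4 and the negative-word ANOVA?

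*Combined protocol and SAP*

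**What the plan says.** The opening design description gives five negativity percentages, two placements and "2 versions of each message condition to allow for the messages to be analyzed as random factors". It explains why there are 18 cells and not 20: "when there is 0% negative portions of a message, it is unnecessary to consider the placement of the negative portions that do not exist". The Participation section repeats the label ("The 18 message conditions are part of a 5x2x2 nested factorial design and are as follows") and lists the messages. Every non-zero percentage appears once with the criticism first and once with it last, in two versions each.

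RQ1, under Hypotheses & Research Questions, asks how ratings "differ depending on whether negative portions of messages occur at the beginning or end of the entire message". RQ2 to RQ4 follow the same pattern. Aim 2 also asks whether placement affects recall.

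Planned Analyses sizes the study on "18 groups, which is the total number of message conditions listed above" and then states "Statistical analyses will consist of 5x2x2 nested factorial ANOVA models". For Aim 1 the models "will test for differences between participants who received the different messages". For Aim 2 they "determine if significant differences occurred in the number of negative words that were recalled across the 18 messages received", with a parenthesis that mentions both position and percentage. No section writes out the model terms or says which line of the ANOVA table answers a placement question.

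**The concern.** The word nested is not tied to a factor. It could mean placement within percentage, message versions within condition, or both. Read literally, a comparison across the 18 messages is a 17-df omnibus test, which isolates neither placement nor percentage. Once the analyst decomposes it, placement can be tested on 1 df (the average beginning-end difference over 20-80%) or on 4 df (any difference at any of the four percentages).

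The 1-df test is stronger when the effect is similar at all percentages. The 4-df test is stronger when the effect sits at one percentage or changes sign. If the choice were made after seeing the results, it could decide the answer to a research question and push its false-positive rate above 5%. Planned Analyses already lets ANOVA become MANOVA, ANCOVA or MANCOVA depending on the data, so one more open choice is a reasonable thing to ask about.

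**Working it through.** **The plan's own figure.** Inputs from Planned Analyses: f = 0.25, alpha = 0.05, power 0.95, 18 groups. With lambda = N × f² = 479 × 0.0625 = 29.94 on F(17, 461), power is 0.9502; at N = 478 it is 0.9496. So 479 reproduces as the 17-df test. The same f and power would need 303 for a 4-df test and 211 for a 1-df test, so the sample-size statement does not show which placement test is meant.

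**Degrees of freedom of the 18-message layout.** Percentage 4 + placement within percentage 4 + versions within condition 9 = 17. The placement 4 df split into a main effect over 20-80% (1 df) and its interaction with percentage (3 df). The sums of squares add: SS(4 df) = SS(1 df) + SS(3 df). A table with both lines therefore contains everything in the 4-df test.

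**Messages fixed, N = 479, equal allocation.** Each condition has m = 479/9 = 53.2 participants. Let p be the beginning-end differences in SD units at 20, 40, 60 and 80% (assumed). Then lambda4 = sum(p²) × m/2 and lambda1 = 4 × mean(p)² × m/2. Power is from noncentral F on 461 error df, and disagreement is from simulation.

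| Assumed pattern | lambda1 | lambda4 | Power, 1 df | Power, 4 df | Disagree |
|---|---|---|---|---|---|
| No effect | 0 | 0 | 0.05 | 0.05 | 7% |
| Uniform 0.25 | 6.65 | 6.65 | 0.73 | 0.51 | 25% |
| Uniform 0.50 | 26.6 | 26.6 | 0.999 | 0.992 | under 1% |
| 0.5 at one percentage | 1.66 | 6.65 | 0.25 | 0.51 | 35% |
| +0.4, +0.2, -0.2, -0.4 | 0 | 10.6 | 0.05 | 0.74 | 70% |

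**Messages random, as the design description intends.** A message mean has variance tau² + 18/479 in residual-variance units, and the error term has 9 df. Disagreement for assumed tau² of 0, 2% and 5% of residual variance:

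| Assumed pattern | 0 | 2% | 5% |
|---|---|---|---|
| No effect | 6% | 6% | 6% |
| Uniform 0.25 | 32% | 27% | 21% |
| Uniform 0.50 | 9% | 22% | 32% |
| 0.5 at one percentage | 23% | 18% | 14% |
| Sign change | 46% | 31% | 21% |

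The fixed-message figures are thus too high for the sign-change case (70%) and too low for the uniform 0.50 case (under 1%).

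**False positives if either test may be reported.** P(either) = (P1 + P4 + P(disagree))/2. Messages fixed: (0.05 + 0.05 + 0.069)/2 = 0.0845, about 8.5%. Messages random: about 8.1% by simulation. For four independent ratings, one named test gives 1 - 0.95⁴ = 18.5% and either test gives 1 - 0.9155⁴ = 29.8%. With an assumed rating correlation of 0.8, the figures are about 11% and 19%. Much of each either-test total comes from running four uncorrected tests, which is a separate matter.

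**What the text favours.** The research questions pose a two-level comparison and do not mention percentage. The design description lists placement as a factor with two levels. The Participation list pairs first and last at every non-zero percentage, and the words mean the same at each. Placement is therefore crossed with percentage over 20-80% and undefined at 0%, which gives a main effect and an interaction. Two versions of each condition can only be nested in conditions.

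**The case for a change.** The best case for a change is that placement is the subject of all four research questions and part of Aim 2, yet no contrast is named. With no placement at 0%, the terms that software prints depend on how the model is coded. The word nested supports placement within percentage as well as anything else, and the open form of the questions admits effects that vary by percentage. One sentence would settle it without touching data, messages or the 479.

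The gap itself stands, and so do the 8% figure and its arithmetic. The step from gap to defect does not. The excess over 5% arises only if the analyst picks the test after seeing the results, and nothing in the plan directs that. The research questions are non-directional and separate from the hypotheses. The largest disagreement needs differences that average exactly zero, a pattern nothing in the documents suggests. An ordinary factorial table would also reveal it, because the 3-df interaction has power 0.79 there (messages fixed, N = 479) against 0.74 for the 4-df test.

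The extension to negative-word counts rests on wording alone. The calculations assume normal ratings with equal variances, which word counts from short recall need not follow, and H7 concerns percentage only.

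**Conclusion.** No change is needed. The plan leaves out a detail that an analyst would fill sensibly: percentage on 4 df including 0%, beginning versus end over 20-80% on 1 df, their interaction on 3 df, and versions within condition as the random error term that the design description implies. The alternative 4-df test is equally valid. Choosing between them means writing down a preference; it does not correct a wrong rule, and neither choice gains power in general.

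The size of the issue is a per-question false-positive rate of about 8% instead of 5%, and only under selection after the results are known. Disagreement between the tests runs from 6% with no effect to 46% across the random-message scenarios. These figures rest on assumed placement effects, assumed message variance, equal allocation and N = 479.

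The 5% level of either test also depends on the error term. If messages vary (assumed intraclass correlation 0.01 to 0.05) and residual error is used, the true level is 0.08 to 0.21 on 1 df and 0.11 to 0.41 on 4 df. That is a separate question from which placement test to report. H1-H4 need the same decomposition, since a literal 17-df comparison would not isolate percentage either; the reading that serves them serves placement too.

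### Covariates enter the Aim 1 models only if found significant, and even then optionally, so the analysis is chosen after seeing the data; they should be fixed in advance

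*Combined protocol and SAP*

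**What the plan says.** Under Planned Analyses, Aim 1 is tested with four nested ANOVA models or a MANOVA. On covariates the plan says that "if significant covariates (such as age or times since diagnosis) are found, the ANOVA/MANOVA could become an ANCOVA or MANCOVA". It does not say how significance is judged, at what level, from which closed list of variables, or whether one decision serves all four outcomes. Nothing is said about covariates for the Aim 2 model of negative words recalled.

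Under Participation, time since initial diagnosis, age and cancer site are self-reported before the message is shown, and the message is then assigned at random.

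Three statements bear on time since diagnosis. Under Recruitment and Eligibility, patients qualify with a "diagnosis of breast, prostate, thoracic, or digestive cancer in the past 3 years". Under Participation, every respondent is told to "imagine receiving a written message of support from this person in the days after initially being diagnosed with cancer". The introduction calls emotional support a "particularly useful form of support in the months following a cancer diagnosis". No interaction or subgroup analysis by time since diagnosis is planned for any hypothesis.

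On sample size: "The suggested sample size provided by G*POWER was 479", and "a power analysis using these same parameters but for an ANCOVA also yielded a suggested samples size of 479".

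**The concern.** Two features of the covariate sentence combine badly. Entry depends on what the data show, and acting on the result is left to discretion. The model behind H1 to H4 and RQ1 to RQ4 is therefore not fixed before the outcomes are known. It can be an ANOVA for one rating and an ANCOVA for another, and both p-values are there to choose from. If the analyst finds a strong predictor but keeps the ANOVA, the study also gives up precision that it has already paid for.

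There is a related gap in scope. Respondents may be anywhere up to 3 years from diagnosis, yet all answer as if days from it. Entering time since diagnosis as a covariate would adjust the ratings for it. It would not show whether the effect of percentage negative changes with distance from diagnosis; only an interaction, or estimates by time, would do so.

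**Working it through.** **Inputs.** From Planned Analyses: f = .25, alpha .05, power .95, 18 groups, N = 479. From Recruitment and Eligibility: 800 to be recruited, four eligible cancer groups. The share of outcome variance explained by any covariate (R², within groups) is not in the documents, so a range is assumed.

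**1. The plan's own figure.** For the 18-group F test, λ = N·f² = 479 × .0625 = 29.94 on 17 and 461 df. Power is .9502, and 479 is the smallest N that reaches .95. With 1, 2, 3 or 5 covariate df the answer is still 479. Time (1 df), age (1 df) and cancer site in four groups (3 df) use 5, so error df fall from 461 to 456. The same f was entered both times. The equal figure therefore shows only that the lost df cost nothing; it credits no gain from adjustment.

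**2. What the rule costs if it is followed.** The chance that one covariate is significant comes from a noncentral F with λ = N·R²/(1 − R²) on 1 and 460 df. At R² = 1%, λ = 479 × .01/.99 = 4.84. The value of using the covariate, in participants, is N/(1 − R²) − N; at R² = 5% this is 479/.95 − 479 = 25.2.

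| R² (assumed) | Chance found significant | Participants' worth lost if not used | Power at 479 if always adjusted |
|---|---|---|---|
| 1% | 59% | 4.8 | 95.3% |
| 5% | 99.9% | 25.2 | 96.1% |
| 10% | 100% | 53.2 | 97.1% |

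A covariate often missed is worth about 5 participants, and one worth having is almost always found. In 3,000 simulated studies at N = 479 with one covariate, following the rule gave power .540 against .539 for always adjusting (R² 5%), and .560 against .560 (R² 10%). Under the null it rejected 4.4% to 5.3% of the time over R² from 0 to 10%.

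**3. What the open choice costs.** Two null simulations at N = 479 each used five candidate covariates, two of them truly prognostic.
- 3,000 runs: ANOVA 5.0%, ANCOVA with the selected covariates 4.9%, either one significant 6.3%.
- 1,500 runs, the real covariates each explaining about 5% or about 9% of variance, four outcomes with residual correlation .5: either one significant 5.6% and 7.3% per outcome, against 4.3% and 5.1% for ANOVA alone. At least one false positive among the four outcomes: 18.9% and 20.3%, against 14.8% and 13.7%.

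The Monte Carlo standard error near 5% is √(.05 × .95/3000) = 0.4 points, and at most √(.05 × .95/1500) = 0.6 points. About 6 to 7% is as fine a statement as these runs allow.

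**4. What an analysis by time could show.** A percentage-by-time term has 4 df. With the 18 cells, time and the interaction fitted, error df are 479 − 18 − 5 = 456. With λ = N·f², power at 479 is 38% at f = .10, 75% at .15 and 95% at .20. It reaches 80% at f = .159 (at N = 800, f = .123).

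**The case against.** The strongest reply is that the rule does little harm as written. Step 2 bears this out: followed to the letter, it matches always adjusting in power and stays near 5%. A reader might infer that testing covariates for significance in itself wastes precision; the figures do not support that. The inflation in step 3 needs someone to run both models and report the favourable one, which the plan does not propose. It is a risk left open by the wording, of one to two percentage points per hypothesis.

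A reader might also infer that the 3-year window biases the message comparisons, or dilutes a larger effect present soon after diagnosis. The documents do not support either. Messages are assigned at random, so spread in time affects generalisability and not the validity of the comparison. The f of .25 is stated for the whole planned population, the objective and hypotheses concern cancer patients in general, and nothing in the plan says that reactions fade. Nor is the study unable to examine the matter: the variable is collected, and the analysis is simply unplanned.

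What remains is that the sentence is undefined and non-binding, although the variables are known before exposure and can be fixed at almost no cost.

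**Conclusion.** The point holds as a matter of prespecification. The covariate rule leaves the Aim 1 model open until the outcomes are seen and lets it vary between outcomes. If either model may be reported, the false-positive rate is about 6 to 7% per hypothesis instead of 5%, given the assumed number, strength and correlation of covariates and outcomes. Precision suffers only if a prognostic covariate is found and the optional step is not taken: about 25 participants' worth at R² 5% and 53 at 10%, both assumed. These are modest sizes, but wholly avoidable.

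On time since diagnosis, the gap is one of scope. The plan does not set out to show whether the percentage effect varies with it, and an interaction test at 479 is too weak for a non-significant result to settle the question. The limit on interpretation should therefore be stated whatever that test shows.

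**What to change.** Replace the covariate sentence with: *All Aim 1 models and the negative-word model include time since initial diagnosis, age and cancer site as covariates, whatever their significance.*

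Add, labelled secondary and exploratory, the percentage effect with confidence intervals by time since initial diagnosis. State that the interaction test has low power: 80% only for f of about .16 or more at 479.

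State without conditions that the results apply to patients diagnosed within 3 years who are imagining the diagnosis period. Eligibility counts from a diagnosis while the questionnaire counts from the initial one, so the time variable should allow values above 3 years.

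The cost is wording and a few error df (5 if site has four groups). All three variables are already collected, and the required sample size stays at 479.
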